9.5.6 Abuse or Diversion of Study Drug

Adverse events associated with abuse or diversion will be appropriately reported as AEs and monitored per [Section 9.5.1.5.1](#). Abuse is always to be captured as an AE.

During the study, the investigator should be aware of the possibility of abuse or diversion of study drugs and should report any concern about mishandling, abuse, loss, theft, or diversion of study drugs by completing the Potential Abuse-related Medication Handling Event eCRF.

9.5.7 Confirmation of Medical Care by Another Physician

The investigator will instruct subjects to inform site personnel when they are planning to receive medical care by another physician. At each visit, the investigator will ask the subject whether he or she has received medical care by another physician since the last visit or is planning to do so in the future. When the subject is going to receive medical care by another physician, the investigator, with the consent of the subject, will inform the other physician that the subject is participating in the clinical study.

9.6 Data Quality Assurance

This study will be organized, performed, and reported in compliance with the protocol, standard operating procedures, working practice documents, and applicable regulations and guidelines. Site audits will be made periodically by the sponsor's or the CRO's qualified compliance auditing team, which is an independent function from the study team responsible for conduct of the study.

9.6.1 Data Collection

Data required by the protocol will be collected on the eCRFs and entered into a validated data management system that is compliant with all regulatory requirements. As defined by ICH guidelines, the CRF is a printed, optical, or electronic document designed to record all of the protocol-required information to be reported to the sponsor on each study subject.

Data collection on the eCRF must follow the instructions described in the CRF Completion Guidelines. The investigator has ultimate responsibility for the collection and reporting of all clinical data entered on the eCRF. The investigator or designee as identified on Form FDA 1572 (where applicable) must sign the completed eCRF to attest to its accuracy, authenticity, and completeness.

Completed, original eCRFs are the sole property of Eisai and should not be made available in any form to third parties without written permission from Eisai, except for authorized representatives of Eisai or appropriate regulatory authorities.

9.6.2 Clinical Data Management

All software applications used in the collection of data will be properly validated following standard computer system validation that is compliant with all regulatory requirements. All data, both eCRF and external data (eg, laboratory data), will be entered into a clinical system.

Electronic source (eSource) methodology may be used for some of the clinical efficacy assessments performed in this study.

9.7 Statistical Methods

All statistical analyses will be performed by the sponsor or designee. Statistical analyses will be performed using SAS software or other validated statistical software as required.

All statistical tests will be based on the 5% (2-sided) level of significance, except for the Bayesian methods on the primary endpoint.

9.7.1 Statistical and Analytical Plans

The statistical analyses of study data are described in this section. Further details of the analytical plan will be provided in the statistical analysis plan, which will be finalized before the first interim efficacy analysis.

9.7.1.1 Study Endpoints

See [Section 9.2.3](#) for a discussion of the rationale for the selection and clinical relevance of the primary study endpoint. Further information on the derived ADCOMS is described in [Section 9.5.1.3.1](#).

9.7.1.1.1 PRIMARY ENDPOINT

- Change from baseline in the derived ADCOMS at 18 months of treatment in MCI/Prodromal subjects

9.7.1.1.2 SECONDARY ENDPOINTS

Change from baseline in:

- Total hippocampal atrophy at 12 and 18 months of treatment in MCI/Prodromal subjects as measured by vMRI
- CSF A β (1-x) after 4 weeks and 18 months of treatment in MCI/Prodromal subjects
- The derived ADCOMS at 18 months of treatment in mild AD subjects

9.7.1.1.3 EXPLORATORY ENDPOINTS

Change from baseline in:

- The derived ADCOMS at 12 months of treatment in MCI/Prodromal and mild AD subjects
- Total hippocampal volume at 12 and 18 months of treatment in mild AD subjects as measured by vMRI
- CSF A β (1-42) after 4 weeks and 18 months of treatment in MCI/Prodromal subjects
- CSF A β (1-x) and A β (1-42) after 4 weeks and 18 months of treatment in mild AD subjects
- The following clinical assessments at 12 weeks and at 6, 9, 12, 15, 18, 19, and 21 months: ADAS-cog, CDR, MMSE, ISLT, CBB, and FAQ in MCI/Prodromal and mild AD subjects
- CSF biomarkers of neurodegeneration (eg, tau and p-tau) at 18 months of treatment in MCI/Prodromal and mild AD subjects
- Plasma and CSF amyloid, and CSF BACE1 measurements after 4 weeks and 18 months of treatment, and during posttreatment follow-up in MCI/Prodromal and mild AD subjects
- Left and right hippocampal, whole brain, and total ventricular volume at 6, 12 and, 18 months in MCI/Prodromal and mild AD subjects as measured by vMRI
- Brain amyloid levels as measured by amyloid PET at 18 months in MCI/Prodromal and mild AD subjects
- The population PK parameters of E2609 including the effect of intrinsic and extrinsic factors (including *NAT2* phenotype) in MCI/Prodromal and mild AD subjects

9.7.1.2 Definitions of Analysis Sets

- The Randomized Set is the group of subjects who are randomized to study drug.
- The Safety Analysis Set is the group of subjects who receive at least 1 dose of study drug and have at least 1 postdose safety assessment.
- The Full Analysis Set (FAS) is the group of randomized subjects who receive at least 1 dose of study drug and have baseline and at least 1 postdose primary efficacy measurement.
- The Per Protocol (PP) Analysis Set is the subset of subjects in the FAS who sufficiently comply with the protocol. The PP Analysis Set will be used to conduct a sensitivity analysis of the primary efficacy endpoint. Details of the evaluability criteria will be determined before database lock and treatment unblinding, and will be specified in the statistical analysis plan.
- The PK Analysis Set is the group of subjects with at least 1 quantifiable E2609 plasma concentration accompanied by a documented dosing history.
- The PD Analysis Set is the group of subjects who have a baseline PD measurement and at least 1 posttreatment PD measurement.

9.7.1.3 Subject Disposition

The number of subjects screened, the number (percent) of subjects who failed screening, and the reasons for screen failure will be summarized, based on data reported on the Screening Disposition eCRF. The distribution of the number of randomized subjects enrolled by each site will be summarized for each randomized treatment group. The primary reasons for screen failures (did not meet inclusion or met exclusion criteria, AE, lost to follow-up, withdrawal of consent, and other) will be presented.

Study Completion: The number (percent) of randomized and treated subjects who completed the study and who withdrew from the study will be summarized according to the primary reason for discontinuation and secondary reason(s) for discontinuation, based on data reported on the Subject Disposition (Study Phase) CRF. The number (percent) will be presented by treatment group and total for subjects; randomized, not treated, treated, who completed the study, and withdrew from the study. The primary reasons for discontinuation from the study are: AE, lost to follow-up, subject choice, withdrawal of consent, pregnancy, study terminated by sponsor, and other. The secondary reasons for discontinuation from the study are: AE, subject choice, and other.

Completion of Study Treatment: The number (percent) of randomized and treated subjects who completed study drug and who discontinued from study drug will be summarized according to the primary reason for discontinuation and also according to secondary reason(s) for discontinuation, based on data reported on both the Subject Disposition (Study Phase) eCRF and ED from Study Drug eCRF. The number (percent) will be presented by treatment group and total for subjects; randomized, not treated, treated, who completed study drug, and discontinued from study drug. The primary reasons for discontinuation from the study drug are: AE, lost to follow-up, subject choice, withdrawal of consent, pregnancy, study terminated by sponsor, inadequate therapeutic response, and other. The secondary reasons for discontinuation from the study are: AE, subject choice, and other.

9.7.1.4 Demographic and Other Baseline Characteristics

Demographic and other baseline characteristics for the Safety Analysis Set and FAS will be summarized for each treatment group using descriptive statistics. Continuous demographic and baseline variables include age, MMSE and FAQ; categorical variables include sex, age group (≤ 65 years, age > 65 years), race, ethnicity, *ApoE4* status (positive or negative), prior treatment with AChEIs or memantine (no or yes), and clinical subpopulation (MCI/Prodromal AD or mild AD).

9.7.1.5 Prior and Concomitant Therapy

All investigator terms for medications recorded in the eCRF will be coded to an 11-digit code using the World Health Organization Drug Dictionary (WHO DD) (Mar 2014). The number (percentage) of subjects who took prior and concomitant medications will be summarized on the Safety Analysis Set by treatment group, Anatomical Therapeutic Chemical class, and WHO DD preferred term. Prior medications will be defined as medications that stopped

before the first dose of study drug. Concomitant medications will be defined as medications that (1) started before the first dose of study drug and were continuing at the time of the first dose of study drug, or (2) started on or after the date of the first dose of study drug up to the date of the last dose. All medications will be presented in subject data listings.

Medications taken within the 12-week Follow-Up period will also be recorded.

9.7.1.6 Efficacy Analyses

MCI/Prodromal Cohort

The study in the MCI/Prodromal cohort is based on Bayesian adaptive design. Frequent interim analyses will be performed to assess the probability of early success and futility and to make early stopping decisions. Response adaptive randomization will be used to update the randomization probability among treatment groups at each interim analysis. Key definitions relevant to the Bayesian aspects of the adaptive design are given below.

Study Definitions

- **Maximum Effective Dose (d_{Max}):** The dose that achieves the greatest treatment effect.
- **ED₉₀:** The lowest dose that achieves at least 90% of the d_{Max} treatment effect in the derived ADCOMS.
- **Early Success:** The study in the MCI/Prodromal cohort will meet early success criteria if the probability that the ED₉₀ at 18 months of treatment achieves 25% improvement over placebo is at least 80%. Early success is achieved before all MCI/Prodromal subjects complete 18 months of treatment and can only be determined after at least 200 MCI/Prodromal subjects have been randomized. If early success is declared before full randomization, the randomization of new MCI/Prodromal subjects will stop but subjects already randomized into the study will receive the full 18 months of treatment (following confirmation from the Sponsor's Senior Management).
- **Futility:** The study in the MCI/Prodromal cohort will meet statistical futility criteria if the probability that the ED₉₀ is better than placebo by the clinically significant difference of 25% is less than 5% at 18 months of treatment. The statistical futility boundary is binding; if the statistical futility boundary is crossed the study will be considered to have failed.
- **Study Success:** The study in the MCI/Prodromal cohort will be considered a success if an ED₉₀ at 18 months treatment has at least an 80% probability of achieving 25% improvement over placebo at either an interim analysis or at the final analysis.

The Mild AD Cohort

The analysis of the Mild AD cohort is based on the group sequential design. Interim analyses in the Mild AD cohort will only be performed after the MCI/Prodromal cohort

crosses the early success boundary. The early efficacy signal based on the change from baseline of ADCOMS at 18 months is defined as crossing the interim-analysis boundaries for overwhelming efficacy in the mild AD population. The O'Brien-Fleming (OF) boundaries based on Lan-DeMets alpha spending function will be used to assess overwhelming efficacy. The corresponding OF boundaries based on P values will be 0.076, 0.0221, and 0.0423 for the first, second, and final analyses, respectively, according to 2 planned interim analyses at the 60% and 80% information fraction.

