9.7.2.2 Sample Size Rationale for the Mild AD Cohort

ADCOMS at Month 18

The null hypothesis is that there is no difference between active dose and placebo. There are 2 null hypotheses corresponding to 2 active doses. The alternative hypothesis is that at least 1 null hypothesis is false. The null hypotheses will be tested using Dunnett's test with 2-sided alpha of 0.05 as described for the mild AD cohort in [Section 9.7.1.6.2](#). The statistical power was estimated through simulation for the dose-response assumption that the percent reduction in change from baseline of ADCOMS at 18 months compared with placebo would be 33% and 50% corresponding to the 2 doses, respectively. The estimated power for the actual planned 200 mild AD subjects is at least 80% assuming a 2-sided alpha of 0.05.

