An interim analysis will be conducted for safety when the first 60 MCI/Prodromal subjects have completed 12 weeks of treatment (or discontinue study drug early).

The first Bayesian adaptive interim analysis will be conducted when 100 MCI/Prodromal subjects have been randomized into the study (ie, 60 subjects from Stage A of the study and the first 40 subjects from Stage B of the study). Further interim efficacy analyses will be conducted after each additional 50 MCI/Prodromal subjects have been randomized, to a maximum of 500 MCI/Prodromal subjects (ie, at 100, 150, 200, 250, 300, 350, 400, 450,

500 subjects randomized). If the study reaches full randomization, additional interim analyses will be conducted every 3 months until all subjects complete 18 months of treatment. The study will be monitored for futility at each interim analysis. Starting at the interim analysis for 200 subjects, the study will be monitored for success at each interim analysis. Each interim analysis will be conducted on data for the derived ADCOMS.

In addition, at each interim efficacy analysis, response adaptive randomization will be used to update the allocation of new subjects between placebo and active doses according to a predefined automated algorithm.

The Mild AD Cohort

A group sequential design will be used for the mild AD cohort. This design includes 3 looks, 2 interim looks (when 60% and 80% information fractions are achieved) and 1 final look. The information fraction is the number of assessments in all treatment arms divided by the total number of expected assessments. Interim analyses will be performed after the MCI/Prodromal cohort crosses the early success boundary. The corresponding efficacy boundaries will be 0.076, 0.022, and 0.0423 for the first, second, and final analyses, respectively. If the actual information fraction during the interim analyses is different from 60% or 80% at the interim, the efficacy boundaries will be adjusted based on the actual information fraction.

If early success in the MCI/Prodromal cohort is not achieved before the final analysis that is performed when all subjects have completed 18 months treatment, then only a final analysis will be performed in mild AD subjects. In the event of futility in the MCI/Prodromal cohort, an analysis will be performed for the mild AD cohort based on the data for mild AD subjects available at that time.

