- **Futility:** The study in the MCI/Prodromal cohort will meet statistical futility criteria if the probability that the ED₉₀ is better than placebo by the clinically significant difference of 25% is less than 5% at 18 months of treatment. The statistical futility boundary is binding; if the statistical futility boundary is crossed the study will be considered to have failed.
- **Study Success:** The study in the MCI/Prodromal cohort will be considered a success if an ED₉₀ at 18 months treatment has at least an 80% probability of achieving 25% improvement over placebo at either an interim analysis or at the final analysis.

The Mild AD cohort: The analysis of the Mild AD cohort is based on the group sequential design. Interim analyses in the Mild AD cohort will only be performed after the MCI/Prodromal cohort crosses the early success boundary. The early efficacy signal based on the change from baseline of ADCOMS at 18 months is defined as crossing the interim-analysis boundaries for overwhelming efficacy in the mild AD population. The O'Brien-Fleming (OF) boundaries based on Lan-DeMets alpha spending function will be used to assess overwhelming efficacy. The corresponding OF boundaries based on P values will be 0.076, 0.0221, and 0.0423 for the first, second, and final analyses, respectively, according to 2 planned interim analyses at the 60% and 80% information fraction.

Analysis for the primary endpoint

The primary analysis will be based on MCI/Prodromal subjects from the FAS with the prespecified censoring rule applied. The primary endpoint is the change from baseline to 18 months in the derived ADCOMS. The dose-response of the primary endpoint is modelled with a first-order normal dynamic linear model, where Normal and Inverse-Gamma priors are used. The primary efficacy analysis will calculate the Bayesian posterior probability that the dose identified is the most likely ED₉₀ dose that achieves 25% improvement over the placebo arm. At each interim analysis and the final analysis, 2 Bayesian probabilities will be summarized for each active dose: the probability it is the ED₉₀ dose and the probability of achieving 25% improvement over the placebo arm.

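### The first mild AD interim boundary is printed as 0.076; the method the protocol names gives 0.0076

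*Protocol*

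**What the plan says.** Section 9.7.1.6 describes a group sequential design for the mild AD cohort on the change in ADCOMS at 18 months. O'Brien-Fleming "boundaries based on Lan-DeMets alpha spending function will be used to assess overwhelming efficacy", with looks set "according to 2 planned interim analyses at the 60% and 80% information fraction" and a final analysis. The numerical boundaries follow: "The corresponding OF boundaries based on P values will be 0.076, 0.0221, and 0.0423 for the first, second, and final analyses". Crossing an interim boundary is what defines the early efficacy signal in this cohort.

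Section 9.7.3 repeats the figures with the second one rounded: "The corresponding efficacy boundaries will be 0.076, 0.022, and 0.0423 for the first, second, and final analyses". The synopsis, in its paragraph on efficacy analyses, has "The corresponding OF boundaries based on P values will be 0.076, 0.0221, and 0.0423", and its paragraph on interim analyses prints 0.076 again. The protocol file contains the texts of Sections 9.7.1.6 and 9.7.3 twice, and 0.076 stands in both copies. The value 0.0076 appears nowhere.

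**The concern.** O'Brien-Fleming nominal P-value boundaries start strict and relax from look to look. The printed sequence starts at 0.076, drops to 0.0221 and rises to 0.0423, so the earliest look, with the least information, is the easiest to pass. The first value also exceeds the total 5% available for all three looks together. The figure therefore contradicts the method named in the same paragraph.

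The number is the decision threshold for this cohort. Followed literally, a result of P = 0.07 at 60% information, which would fail even an ordinary 5% test, would be declared overwhelming efficacy. According to the Introduction (Section 7), the results of this study are to guide the decision to enter Phase 3 and the choice of doses, so a false signal in mild AD could carry weight. Dunnett's method in Section 9.7.1.6.2 deals with the two doses and not with the repeated looks, so it does not repair this.

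**Working it through.** **Inputs**

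- Overall level: two-sided 0.05. Section 9.7: "All statistical tests will be based on the 5% (2-sided) level of significance, except for the Bayesian methods on the primary endpoint". Section 9.7.2.2, for this cohort: "The estimated power for the actual planned 200 mild AD subjects is at least 80% assuming a 2-sided alpha of 0.05".
- Method and looks: Lan-DeMets spending of O'Brien-Fleming type at t = 0.6, 0.8 and 1.0 (Section 9.7.1.6).

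**Step 1: alpha spent.** With 0.025 in each tail, the cumulative two-sided alpha is

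α(t) = 4 × [1 − Φ(z₀.₉₈₇₅ / √t)], where z₀.₉₈₇₅ = 2.2414.

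- t = 0.6: 2.2414 / 0.7746 = 2.894, so α = 0.00762
- t = 0.8: 2.2414 / 0.8944 = 2.506, so α = 0.02442
- t = 1.0: α = 0.0500

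**Step 2: boundaries.** At the first look the nominal P value equals the alpha spent. The later boundaries were solved by recursive numerical integration so that each look spends its increment.

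| Look | Z | Nominal two-sided P | Printed |
|---|---|---|---|
| 60% | 2.669 | 0.0076 | 0.076 |
| 80% | 2.289 | 0.0221 | 0.0221 |
| 100% | 2.031 | 0.0423 | 0.0423 |

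The second and third figures match to four decimals, which identifies the convention that was used. Under that convention the first boundary is 0.0076.

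**Step 3: could another convention give 0.076?** None of those tried does.

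| Convention | 60% | 80% | 100% |
|---|---|---|---|
| One spending function applied to two-sided 0.05 | 0.0114 | 0.0244 | 0.0392 |
| One-sided 0.05 (one-sided P) | 0.0114 | 0.0251 | 0.0410 |
| One-sided 0.025 (one-sided P) | 0.0038 | 0.0111 | 0.0211 |
| Two-sided 0.10 | 0.0228 | 0.0501 | 0.0821 |
| Classical O'Brien-Fleming, two-sided 0.05 | 0.0085 | 0.0227 | 0.0416 |

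**Step 4: overall type I error.** Probability under the null of first crossing at each look, two-sided, for one test statistic:

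- As printed (0.076 / 0.0221 / 0.0423): 0.0760 + 0.0041 + 0.0166 = 0.0967
- Corrected (0.0076 / 0.0221 / 0.0423): 0.0076 + 0.0168 + 0.0256 = 0.0500

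Reading the printed values as one-sided P values gives 0.093, so that reading does not help. Using 0.022 in place of 0.0221 leaves the corrected total at 0.0500.

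**The case against.** The strongest reply is that the governing rule is stated correctly. The protocol names the method, the alpha and the information fractions, and gives the numbers as derived from them. Anyone who computes the boundary gets 0.0076, and an independent analysis group would probably query a threshold for overwhelming efficacy that is looser than 5%. That is likely, but it relies on someone overruling the protocol: the text does not say that the method prevails over the printed number, and no section prints the right one.

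Section 9.7.3 also has a recalculation clause: "If the actual information fraction during the interim analyses is different from 60% or 80% at the interim, the efficacy boundaries will be adjusted". An interim held at some other fraction would replace the printed value, which narrows the exposure. The clause does nothing for a look held at the planned 60%.

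The stakes are bounded as well. This is a secondary endpoint in a Phase 2 study, the mild AD interim looks open only after the MCI/Prodromal cohort crosses its early success boundary, and the sections quoted attach no stopping rule to a mild AD crossing. These limits stand. They reduce how often the error would matter; they do not make the figure right. The error would apply in the favourable scenario, where a mild AD signal would be most readily acted on.

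**Conclusion.** The first boundary is wrong as printed and should read 0.0076. Taken literally, the printed set nearly doubles the type I error, from 5.00% to 9.67%. That figure assumes that all three looks are held at exactly 60%, 80% and 100% information, that a single test statistic is monitored, and that MCI/Prodromal early success has opened the interim looks. It does not include the two-dose comparison and says nothing about the primary Bayesian analysis, which does not use this boundary. The difference between 0.0221 and 0.022 is rounding only.

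**What to change.** Replace 0.076 by 0.0076 in Section 9.7.1.6, in Section 9.7.3 and in both places in the synopsis, in every copy of the text in force. For consistency, print 0.0221 throughout.

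It would also help to state that, when no mild AD interim is held because MCI/Prodromal early success was not reached, the single final test is made at 0.05. This is a clarification, and the finding does not depend on it.

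The SAP was not seen for this review; its boundaries should be checked against the same three values. The cost is a wording amendment with no effect on patients, procedures or sample size. It should be made before any unblinded mild AD analysis, because a correction after that point would look post hoc.
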